6.4 Treatment compliance

During the Initial Treatment Period and Maintenance Treatment Period of this study, the IMP will be administered in the clinic, and compliance will be determined at the visit by study personnel. Drug accountability must be recorded on the Drug Accountability Form (Section 6.2.1).

If a study participant is noncompliant with the study procedures or medications, in the opinion of the Investigator, then the study participant should be withdrawn as described in Section 7.2.

6.5 Concomitant medication(s)/treatment(s)

Any medications/treatment administered from the time of informed consent to the final study visit will be considered concomitant medication/treatment. This includes medications/treatments that were started before the study and are ongoing during the study.

6.5.1 Permitted concomitant treatments (medications and therapies)

6.5.1.1 Topical medications

The following concomitant topical medications are permitted during the study:

- Study participants may continue to use topical moisturizers or emollients, bath oils, or oatmeal bath preparations for skin conditions during the study, as needed (PRN). Over-the-counter shampoos for the treatment of scalp PSO are also permitted.
- Mild and low potency topical steroids will be permitted for use limited to the face, axilla, and/or genitalia, PRN. These topical medications should not be used within approximately 24 hours prior to study visits requiring IGA and PASI measures.

6.5.1.2 Other medications

Study participants who are receiving an established regimen for depression should remain on stable dosing prior to Baseline and throughout the study. Medication used to treat depression should be stable for 4 weeks prior to Baseline.

6.5.2 Prohibited concomitant treatments (medications and therapies)

For prohibited prior medications, refer to the exclusion criteria (Section 5.2).

Prohibited concomitant medications and therapies are outlined in Table 6-3.

Table 6-3: Prohibited concomitant treatments (medications and therapies)

Drug	Washout period relative to Baseline Visit
Topicals, except for those permitted	2 weeks
Systemic retinoids	1 month
Systemic treatment (nonbiological): systemic immunosuppressant agents (eg, methotrexate, cyclosporine, azathioprine, thioguanine) fumaric acid esters specifically used for the treatment of PSO systemic corticosteroids phototherapy	1 month
Anti-TNFs:	
etanercept (including biosimilar)	1 month
infliximab (including biosimilar) golimumab certolizumab pegol adalimumab (including biosimilar)	3 months
Other biologics and other systemic therapies, eg:	
ustekinumab	3 months
apremilast, tofacitinib	2 weeks
guselkumab	3 months
rituximab	3 months
Anti-IL-17 therapy ^a : secukinumab ixekizumab brodalumab	3 months
Any other antipsoriatic agent (systemic) under investigation (or approved after the protocol is approved)	3 months or 5 half-lives, whichever is greater
Any other antipsoriatic agent (systemic) not listed above	3 months or 5 half-lives, whichever is greater
Any other antipsoriatic agent (topical) under investigation	1 month
Traditional systemic Chinese medicine treatments for PSO and/or PsA	1 month

IL-17=interleukin 17; PsA=psoriatic arthritis; PSO=psoriasis; TNF=tumor necrosis factor

^a Bimekizumab is prohibited per exclusion criteria (Section 5.2).

Study participants who take prohibited medications may be withdrawn from IMP but followed until the SFU Visit. The decision to withdraw a study participant for taking prohibited medications should be made in consultation with the Medical Monitor.

6.5.3 Vaccines

Administration of live (including attenuated) vaccines is not allowed during the conduct of the study and for 17 weeks after the final dose of IMP. Administration of inactivated vaccines is allowed during the study at the discretion of the Investigator in consultation with the Medical Monitor.

Administration of any other type of vaccine that is not a live or inactivated vaccine must be discussed with the Medical Monitor.

6.5.4 Rescue medication

No rescue medication is planned.

6.6 Dose modification

No dose modifications are allowed during the Initial Treatment Period or Maintenance Treatment Period.

6.7 Criteria for study hold or dosing stoppage

UCB reserves the right to temporarily suspend or prematurely discontinue this study either at a single site, multiple sites, or at all sites at any time for reasons, including, but not limited to, safety or ethical issues, inaccurate or incomplete data recording, noncompliance, or unsatisfactory enrollment with respect to quality or quantity.

If the study is prematurely terminated or suspended, UCB (or its representative) will inform the Investigators/institutions and the regulatory authority(ies) of the termination or suspension and the reason(s) for the termination or suspension, in accordance with applicable regulatory requirement(s). The Institutional Review Board (IRB)/Independent Ethics Committee (IEC) should also be informed and provided with the reason(s) for the termination or suspension by the Sponsor or by the Investigator/institution, as specified by the applicable regulatory requirement(s). In addition, arrangements will be made for the return or destruction of all unused IMP and other material in accordance with UCB procedures for the study.

6.8 Treatment after the end of the study

After the end of PS0041, study participants can switch to alternative treatments.

7 DISCONTINUATION OF IMP AND PARTICIPANT DISCONTINUATION/WITHDRAWAL

7.1 Discontinuation of IMP

A study participant should be withdrawn from IMP and will be asked to come back for the SFU Visit 17 weeks after the final dose of IMP if any of the following events occur:

1. Study participant develops an illness that, in the opinion of the Investigator, would interfere with his/her continued participation if the risk of continuing participation outweighs the potential benefit.

2. Study participant develops erythrodermic, guttate, or pustular form of PSO.
3. Study participant is noncompliant with the study procedures or medications in the opinion of the Investigator.
4. Study participant uses prohibited concomitant medications (as defined in Section 6.5.2) that may present a risk to the safety of the study participant or the integrity of the study data, in the opinion of the Investigator and/or the Medical Monitor.
5. Study participant has a clinical laboratory value meeting any of the following criteria:
 - Hepatotoxicity as described in Section 7.1.1.
 - A laboratory value meeting any of the following criteria:
 - Absolute neutrophil count $<1.0 \times 10^3/\mu\text{L}$
 - Absolute lymphocyte count $<0.5 \times 10^3/\mu\text{L}$

A study participant may remain in the study if the result is transient. A retest is required within 1 to 2 weeks at a scheduled or unscheduled visit. If the repeat absolute neutrophil count or absolute lymphocyte count is still below the allowable values, the study participant must be withdrawn. If the repeat absolute neutrophil count or absolute lymphocyte count is above the allowable values, the study participant may continue in the study.

6. There is confirmation of a pregnancy during the study, as evidenced by a positive pregnancy test. See Section 10.4 (Appendix 4) for more information regarding pregnancies.
7. Study participant experiences a severe AE, an SAE, or a clinically significant change in a laboratory value that, in the opinion of the Investigator, merits the discontinuation of IMP and appropriate measures being taken.
8. Study participant considered as having either a suspected new LTBI or who develops an active TB or NTMB infection during the study must be immediately discontinued from IMP, and a PEOT Visit must be scheduled as soon as possible, but not later than the next regular visit.

The study participant must be permanently withdrawn if further examinations result in a diagnosis of active TB or if the study participant is diagnosed with LTBI with no initiation of prophylactic treatment, prematurely discontinues prophylactic treatment, or, in the opinion of the Investigator or Sponsor, is noncompliant with prophylactic TB therapy.

Confirmed active TB is an SAE and must be captured on an SAE Report Form and provided to the Sponsor in accordance with SAE reporting requirements. As with all SAEs, periodic follow-up reports should be completed as described in Section 10.3 (Appendix 3) until such time as the TB infection resolves.

Additional information on TB policies is provided in (Section 8.2.5).

9. Study participants with newly diagnosed IBD during the study must discontinue IMP.
10. Study participant has SIB and/or any evidence of major depression. Study participants **must be referred** immediately to a mental health care professional for further assessment of any SIB and/or any evidence of major depression. Withdrawal is mandatory for suicidal behavior and/or a confirmed diagnosis of severe major depression. Otherwise, a withdrawal decision

will be based on the Investigator's assessment of benefit/risk in consultation with the Medical Monitor.

Investigators should attempt to obtain information on study participants in the case of withdrawal or discontinuation. For study participants considered as lost to follow up, the Investigator should make an effort (≥ 1 phone call and 1 written message to the study participant) and document his/her effort (date and summary of the phone call and copy of the written message in the source documents) to complete the final evaluation. All results of these evaluations and observations, together with a narrative description of the reason(s) for removing the study participant, must be recorded in the source documents. The eCRF must document the primary reason for withdrawal or discontinuation.

Investigators should contact the Medical Monitor, whenever possible, to discuss withdrawal of a study participant in advance.

7.1.1 Potential drug-induced liver injury IMP discontinuation criteria

Study participants with potential drug-induced liver injury (PDILI) must be assessed to determine if IMP must be discontinued. In addition, all concomitant medications and herbal supplements that are not medically necessary should also be discontinued.

Immediate and permanent discontinuation of IMP is required for study participants with either of the following PDILI criteria:

- ALT or AST $\geq 8 \times \text{ULN}$
- ALT or AST $\geq 3 \times \text{ULN}$ and coexisting total bilirubin $\geq 2 \times \text{ULN}$

Immediate discontinuation of IMP is required for study participants with the following PDILI criterion:

- Study participants with ALT or AST $\geq 3 \times \text{ULN}$ who exhibit temporally associated symptoms of hepatitis or hypersensitivity. Hepatitis symptoms include fatigue, nausea, vomiting, and right upper quadrant pain or tenderness. Hypersensitivity symptoms may include fever (without clear alternative cause), rash, or eosinophilia.

If a nondrug-related cause for the symptoms can be confirmed, these study participants may resume IMP administration after discussion with the responsible UCB Study Physician, but only when the requirements for rechallenge with IMP (as provided in Section 10.6 [Appendix 6]) are met.

Study participants with the PDILI criterion below may be allowed to continue on IMP at the discretion of the Investigator:

- Study participants with ALT or AST $\geq 5 \times \text{ULN}$ and $< 8 \times \text{ULN}$, total bilirubin $< 2 \times \text{ULN}$, and no eosinophilia, with no fever, rash, or symptoms of hepatitis (eg, fatigue, nausea, vomiting, right upper quadrant pain or tenderness).

Evaluation of PDILI must be initiated (as described in Section 10.6 [Appendix 6]), with repeat tests performed in 2 weeks. Upon retest, if ALT or AST values have reduced to $< 5 \times \text{ULN}$, the study participant can continue with the study. However, if ALT or AST values remain $\geq 5 \times \text{ULN}$ and $< 8 \times \text{ULN}$ after retest, IMP should be temporarily withheld, and study participant should undergo a repeat test in 2 weeks. If ALT or AST values remain

$\geq 5 \times \text{ULN}$ even after the second retest, then the study participant should be permanently withdrawn from the study and should be followed for PDILI.

If a study participant is unable to comply with the applicable monitoring schedule, IMP must be discontinued immediately.

Investigators should attempt to obtain information on study participants in the case of IMP discontinuation to complete the final evaluation. Study participants with PDILI should not be withdrawn from the study until investigation and monitoring are complete. All results of these evaluations and observations, as well as the reason(s) for IMP discontinuation and study participant withdrawal (if applicable), must be recorded in the source documents. The eCRF must document the primary reason for IMP discontinuation.

Specific assessments and follow-up actions for PDILI are provided in Section 10.6 (Appendix 6).

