When IMP is discontinued, all concomitant medications and herbal supplements that are not medically necessary should also be discontinued. In these cases, the Investigator should also consider dose reduction for medically necessary concomitant medication and consider changing any medically required concomitant medication known to be hepatotoxic to a suitable alternative.

When IMP is stopped due to PDILI (as described in Section 7.1.1), IMP must be permanently discontinued unless a subsequent alternative diagnosis fully explains the hepatic findings. If a subsequent alternative diagnosis fully explains the hepatic findings, and the requirements provided in Section 10.6.2.1 are met, rechallenge with IMP may be appropriate.

The approach to investigate PDILI is summarized in Table 10-3.

Table 10-3: Required investigations and follow up for PDILI

Laboratory value			Immediate		Follow up	
ALT or AST	Total bilirubin	Symptoms ^a of hepatitis or hypersensitivity	Consultation requirements	Actions	Testing	Evaluation
$\geq 3 \times \text{ULN}$	$\geq 2 \times \text{ULN}^b$	N/A	Hepatology consult ^c Medical Monitor must be notified within 24 hours (eg, by laboratory alert) and study participant discussed with Medical Monitor ASAP.	Immediate IMP discontinuation ^d	Essential: Must have repeat liver chemistry values and additional testing completed ASAP (see Section 10.6.3); recommended to occur at the site with HCP.	Monitoring of liver chemistry values at least twice per week until values normalize, stabilize, or return to within Baseline values. ^e
$\geq 3 \times \text{ULN}$	N/A	Yes				
$\geq 8 \times \text{ULN}$	N/A	N/A	Need for hepatology consult to be discussed (required if ALT or AST $\geq 8 \times \text{ULN}$) Medical Monitor must be notified within 24 hours (eg, by laboratory alert) and study participant discussed with Medical Monitor ASAP.			
$\geq 5 \times \text{ULN}$ (and $\geq 2 \times \text{Baseline}$) and $< 8 \times \text{ULN}$	$< 2 \times \text{ULN}$	No	Discussion with Medical Monitor required. Consider need for hepatology consult if there is no evidence of resolution (see	Further investigation – immediate IMP discontinuation not	Essential: Every attempt must be made to have repeat liver chemistry values and additional testing completed within 48 hours at the site with HCP (see Section 10.6.3).	Monitoring of liver chemistry values at least twice per week for 2 weeks. ^e 
• Immediate IMP discontinuation required if liver

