10.6.2.1 IMP restart/rechallenge

Study participants who are immediately discontinued from IMP due to having met certain criteria for PDILI (as described in Section 7.1.1 and Table 10-3), but for whom an alternative diagnosis is confirmed, ie, drug-induced liver injury is excluded, can rarely restart IMP.

Rechallenge with IMP can occur only if ALL of the following requirements are met:

- The results of additional testing and monitoring described in Section 10.6.3 and Section 7.1.1.1 confirm a nondrug-related cause for the abnormal hepatic laboratory parameters and any associated symptoms (ie, a subsequent alternative diagnosis fully explains the hepatic findings).
- No alternative treatment options are available to the study participant.
- The study participant has shown clear therapeutic benefit from the IMP.
- Study participant's ALT or AST elevations do not exceed $\geq 5 \times \text{ULN}$.
- Study participant's total bilirubin is $< 2 \times \text{ULN}$.
- Study participant has no signs or symptoms of hypersensitivity or hepatitis.
- The rechallenge is approved by the UCB Study Physician and a hepatologist. The hepatologist must be external to UCB. It is recommended that the hepatologist be a local hepatology expert or the hepatologist treating the study participant.
- Study participant agrees to the Investigator-recommended monitoring plan and understands his/her individual benefit/risk for restarting IMP and this is adequately documented.

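### Section 7.1.1 makes two liver-injury stops permanent without exception, while Appendix 6 leaves a narrow route to restart open for the same stops

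*Protocol*

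**What the plan says.** Protocol Section 7.1.1 sorts the required stops into two tiers.

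- **First tier:** "Immediate and permanent discontinuation of IMP is required for study participants with either of the following PDILI criteria". The two criteria are ALT or AST ≥8×ULN, and ALT or AST ≥3×ULN together with total bilirubin ≥2×ULN. No exception follows for either.
- **Second tier:** ALT or AST ≥3×ULN with symptoms of hepatitis or hypersensitivity. The stop is immediate but is not called permanent. If a cause other than the drug is confirmed, "these study participants may resume IMP administration after discussion with the responsible UCB Study Physician", subject to the rechallenge requirements in Appendix 6.

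The introduction to Appendix 6 (Section 10.6) defines its scope with the words "When IMP is stopped due to PDILI (as described in Section 7.1.1". For those stops, "IMP must be permanently discontinued unless a subsequent alternative diagnosis fully explains the hepatic findings". It adds that if such a diagnosis exists and "the requirements provided in Section 10.6.2.1 are met, rechallenge with IMP may be appropriate".

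Section 10.6.2.1 speaks of "Study participants who are immediately discontinued from IMP due to having met certain criteria for PDILI (as described in Section 7.1.1 and Table 10-3". Where another cause has been established in such a person, it describes restart as possible but rare. It then sets the threshold: "Rechallenge with IMP can occur only if ALL of the following requirements are met". Eight requirements follow. Section 7.1.4 refers the reader to 10.6.2.1 for restart.

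**The concern.** Section 7.1.1 appears to separate the tiers on purpose: it uses the word permanent for the first tier only and words of resumption for the second tier only. The Appendix 6 introduction does not keep that separation, because its exception attaches to every liver stop in 7.1.1. A participant in the first tier whose findings are later explained by another diagnosis, and who meets all rechallenge requirements, is barred from restart by one text and eligible for it by the other.

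This is a safety stopping rule. Two sites following the protocol could handle such a participant differently, and either course could be recorded as a deviation. There is also a secondary link to the analysis. SAP Section 4.2.2 counts as nonresponders those who permanently withdraw from IMP before Week 16, so whether a stop is final can bear on how a participant is classified.

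**Working it through.** No arithmetic underlies the conflict itself, so the texts are set side by side by criterion.

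| Criterion | Section 7.1.1 | Appendix 6 introduction | Result |
|---|---|---|---|
| ALT or AST ≥8×ULN | Stop at once, permanent, no exception | Permanent, with a conditional exception | Conflict on later restart |
| ALT or AST ≥3×ULN and total bilirubin ≥2×ULN | Stop at once, permanent, no exception | Permanent, with a conditional exception | Conflict on later restart |
| ALT or AST ≥3×ULN with symptoms | Stop at once, conditional resumption | Permanent, with a conditional exception | Consistent |

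The next question is whether another part of the protocol settles the first two rows.

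1. **Table 10-3.** In the available copy, the three stopping rows share one action, an immediate stop, and none is marked permanent. A footnote sends the reader to Section 10.6.2.
2. **Section 10.6.2.** It names immediate and permanent discontinuation as one end of the range of actions, so the category does survive inside Appendix 6. For details it points to Section 7.1.1 and back to Table 10-3, and the table does not say which rows are permanent.
3. **Section 10.6.2.1.** It limits restart to some of the criteria in 7.1.1 and Table 10-3 without saying which.
4. **Precedence.** No rule ranking the body text over the appendix was found, and Sections 7.1.1 and 7.1.4 both rely on Appendix 6 for restart.

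None of these removes the first two criteria from the Appendix 6 exception.

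**Size of any endpoint effect.** The documents give no expected number of such events. Assume 0 to 2 of 120 participants meet one of the two criteria, that is 0% to 2/120 = 1.7%. Cases in which the texts diverge are a subset, because every rechallenge requirement must also be met. One reclassified participant would move the responder proportion by 1/90 = 1.1 percentage points in the bimekizumab arm, or by 1/30 = 3.3 points in the placebo arm. For the co-primary endpoints, that needs an event and an approved restart early enough to affect Week 16 status, followed by responder-level data at Week 16.

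**The case against.** The best defence is that a consistent reading exists. Section 10.6.2.1 cross-refers to 7.1.1, and 7.1.1 names only the symptom group as able to resume, so the unnamed criteria could mean that group alone. Section 10.6.2 keeps permanent discontinuation as a distinct outcome. This reading is possible, and it makes 10.6.2.1 compatible with 7.1.1. It does not reach the sentence in the Appendix 6 introduction, which covers all 7.1.1 stops without a carve-out.

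A second defence is that the rechallenge limits on ALT/AST and bilirubin already exclude the two groups. That holds only if they refer to peak values. The same list requires absence of signs or symptoms; read as history, that would exclude the symptom group that 7.1.1 expressly lets resume. The limits read more naturally as status at the time of rechallenge.

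A third defence is that the practical reach is very small, and this stands. Restart is described as rare. It needs approval by the sponsor's study physician and a hepatologist external to the sponsor, and it requires that the participant have no alternative treatment. Protocol Section 2.2.1 lists several biologics available in China. No site would decide on restart alone.

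Three stronger readings are tempting and not supported:

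- **That Appendix 6 allows restart once an alternative diagnosis is found.** The diagnosis must account completely for the findings and all eight requirements must be met.
- **That every severe liver case has two contradictory answers.** Without such a diagnosis, or with any requirement unmet, both texts give the same answer, and the immediate stop is the same throughout.
- **That the answer decides the endpoint.** Missing Week 16 data also count as nonresponse, and events after Week 16 cannot affect the co-primary endpoints. Protocol Section 9.3.1 refers to withdrawal from IMP without the qualifier permanent; that difference from the SAP is a separate matter.

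**Conclusion.** The inconsistency is real and narrow. For ALT or AST ≥8×ULN, and for ALT or AST ≥3×ULN with total bilirubin ≥2×ULN, Section 7.1.1 rules out restart and the Appendix 6 introduction leaves it conditionally open. It concerns only a possible later restart when all rechallenge requirements are met. It is a wording conflict between sections, not a flaw in the trial's design. The reason to act is clarity in a safety rule; the effect on Week 16 responder status is indirect and, on the assumed event range, at most a participant or two. The conclusion rests on reading the Appendix 6 scope as covering all 7.1.1 stops, as its words say. No view is taken on which rule is right.

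**What to change.** Reconcile Section 7.1.1, the introduction to Section 10.6, Table 10-3, Section 10.6.2 and Section 10.6.2.1. Each should state, criterion by criterion and in identical words, whether restart is possible. In particular, Section 10.6.2.1 should name the criteria to which it applies, and Table 10-3 should show the status of each stopping row. The content is for the sponsor's safety physician to decide. The cost is a wording change to the protocol; this point requires no change to sample size, assessments or analysis methods.

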7.1.1.1 Follow-up evaluation

Potential drug-induced liver injury events require follow-up monitoring as described in Table 10-3. Monitoring should continue until liver chemistry values normalize, stabilize, or return to Baseline. Determination of stabilization is at the discretion of the Investigator in consultation with the hepatologist (as applicable) and Medical Monitor and UCB Study Physician, as needed.

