Table 10-3: Required investigations and follow up for PDILI

Laboratory value			Immediate		Follow up	
ALT or AST	Total bilirubin	Symptoms ^a of hepatitis or hypersensitivity	Consultation requirements	Actions	Testing	Evaluation
			follow-up requirements). ^c	
required (see Section 10.6.2).
 
IMP discontinuation required if any of the following occur:
 
 • Study participant cannot comply with monitoring schedule. • Liver chemistry values continue to increase. • Liver chemistry values remain $\geq 5 \times \text{ULN}$ (and $\geq 2 \times \text{Baseline}$) after 4 weeks of monitoring without evidence of resolution. 		
chemistry values continue to increase.
 
After 2 weeks of monitoring liver chemistry values:
 
 • ALT or AST remains $\geq 5 \times \text{ULN}$ to $< 8 \times \text{ULN}$, IMP should be temporarily withheld, and study participant should undergo repeat test in 2 weeks. • Continue IMP if ALT or AST values $< 5 \times \text{ULN}$; continue to monitor at least twice per week until values normalize, stabilize, or return to within Baseline values. • If ALT or AST remains $\geq 5 \times \text{ULN}$ after second retest, immediate IMP discontinuation required. • Continue to monitor until values normalize, stabilize, or return to within Baseline values.^c

ALP=alkaline phosphatase; ALT=alanine aminotransferase; ASAP=as soon as possible; AST=aspartate aminotransferase; HCP=health care practitioner; IMP=investigational medicinal product; N/A=not applicable; PDILI=potential drug-induced liver injury; ULN=upper limit of normal

Table 10-3: Required investigations and follow up for PDILI

Laboratory value			Immediate		Follow up	
ALT or AST	Total bilirubin	Symptoms ^a of hepatitis or hypersensitivity	Consultation requirements	Actions	Testing	Evaluation

^a Hepatitis symptoms include fatigue, nausea, vomiting, and right upper quadrant pain or tenderness; hypersensitivity symptoms include eosinophilia, rash, and fever (without clear alternative cause).

^b If the study participant also has $\geq 2 \times \text{ULN}$ ALP, the possibility of an indication of biliary obstruction should be discussed with the Medical Monitor.

^c Details provided in Section 10.6.1. The local hepatologist is the expert usually consulted by the treating physician for assessment and management of potential hepatic disease. This would usually be a hepatologist but may be a gastroenterologist.

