^d Details are provided in Section 10.6.2.

^e Unless an alternative monitoring schedule is agreed by the Investigator and responsible UCB Study Physician, Determination of stabilization is at the discretion of the Investigator in consultation with the hepatologist (as applicable) and responsible UCB Study Physician, as needed.

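### For symptom-free ALT or AST of 5 to below 8 × ULN, protocol Section 7.1.1 and Table 10-3 give conflicting rules on stopping IMP and on study withdrawal, and Table 10-3 also disagrees with itself

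*Protocol*

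**What the plan says.** Two places in the protocol deal with this laboratory band: Section 7.1.1, and the last row of Table 10-3 in Section 10.6 (Appendix 6).

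**Section 7.1.1.** The Investigator may let the participant stay on IMP. Evaluation starts under Section 10.6, "with repeat tests performed in 2 weeks". Below 5 × ULN at that retest, the participant continues. If the value is still 5 to below 8 × ULN, IMP is held temporarily and the test is repeated 2 weeks later. If it is still at or above 5 × ULN at the second retest, the participant is to leave the study permanently and be followed for PDILI. Later in the same section: "Study participants with PDILI should not be withdrawn from the study until investigation and monitoring are complete".

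**Table 10-3.** The row adds an entry condition of at least 2 × Baseline and requires discussion with the Medical Monitor. On testing: "Every attempt must be made to have repeat liver chemistry values and additional testing completed within 48 hours at the site with HCP". On follow-up: "Monitoring of liver chemistry values at least twice per week for 2 weeks". The 2-week rule matches Section 7.1.1: continue below 5 × ULN, otherwise hold IMP and retest in 2 weeks. Both the Actions and the Evaluation columns also require IMP discontinuation in a further case: "Liver chemistry values continue to increase". After a second retest at or above 5 × ULN, the Evaluation column requires IMP discontinuation with monitoring carried on. The Actions column states its own 4-week stop with two extra limits: at least 2 × Baseline, and no sign of resolution.

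**Cross-references.** Section 7.1.1.1 says PDILI events "require follow-up monitoring as described in Table 10-3". Section 10.6.2 cites Section 7.1.1 and Table 10-3 together for the immediate action and does not rank them.

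**The concern.** The same liver finding can lead to different decisions depending on which page a site opens. Three decisions are exposed: whether a rising value means a temporary hold or an end to IMP, whether a failed second retest ends IMP or ends study participation, and whether a value that is high but falling at 4 weeks requires a stop at all.

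The first stake is consistent protection of participants with a liver signal. The second is the data. The protocol treats IMP discontinuation (Section 7.1) and study withdrawal (Section 7.2) as separate events. The SAP (Section 4.2.2) makes permanent withdrawal from IMP before Week 16 a nonresponse on both co-primary endpoints.

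**Working it through.** The plan states no figure on this point. The check sets the two texts side by side and runs example values (in multiples of ULN, no symptoms, bilirubin below 2 × ULN) through each rule. The values are illustrations.

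| Situation | Section 7.1.1 | Table 10-3, Actions | Table 10-3, Evaluation |
|---|---|---|---|
| In band and rising at 2 weeks | Temporary hold, retest in 2 weeks | IMP discontinuation | IMP discontinuation (rising values), and also temporary hold (still in band) |
| At or above 5 at second retest | Permanent withdrawal from study, PDILI follow-up | IMP discontinuation if also ≥2 × Baseline and not resolving | IMP discontinuation, monitoring continues |

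**1. Rising value.** First value 5.5, climbing through the interim tests to 7.0 at 2 weeks. Since 5 ≤ 7.0 < 8, Section 7.1.1 gives a temporary hold. The rising-value rule in Table 10-3 gives discontinuation. The Evaluation column also contains the hold rule and does not say which line prevails.

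**2. Second retest failed.** Values stay at 6.0 throughout. Section 7.1.1 withdraws the participant from the study; the table's Evaluation column stops IMP and keeps monitoring. Section 7.1.1 also says no study withdrawal until monitoring is complete. Section 10.6 allows IMP to resume, under the conditions in Section 10.6.2.1, if another diagnosis fully explains the finding. Permanent study withdrawal would close that route.

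**3. High but falling.** 7.5 at first, 5.2 at 4 weeks, Baseline 1.0 (so 2 × Baseline = 2.0 and that limit is met). Section 7.1.1: study withdrawal, since 5.2 ≥ 5. Actions column: no stop required if the fall counts as resolution. Evaluation column: immediate IMP discontinuation. One participant, three answers.

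**4. Reach of the Baseline condition.** It changes who enters the row only if 2 × Baseline > 5, so Baseline > 5 / 2 = 2.5. Exclusion criterion 19 excludes ALT or AST at or above 3.0 × ULN at Screening. If Baseline stays under that limit, 2 × Baseline < 6.0. The gap is therefore Baseline above 2.5 and below 3.0, with an on-study value from 5 to below 2 × Baseline. Example: Baseline 2.8, on-study 5.3. It meets Section 7.1.1, but 5.3 < 2 × 2.8 = 5.6, so no row of Table 10-3 applies.

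**5. Reach into the primary endpoint.** Between Baseline and Week 16, the Schedule of Activities shows routine chemistry only at Week 4. A finding there puts the 2-week decision near Week 4 + 2 = 6 and the second retest near Week 6 + 2 = 8, both before Week 16. A temporary hold is not permanent withdrawal under SAP Section 4.2.2; discontinuation that stays permanent is. One participant who would otherwise respond moves the response rate by 1/90 = 1.1 percentage points in the bimekizumab arm or 1/30 = 3.3 points in the placebo arm.

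**The case against.** The strongest reply is that the two texts are meant to be read together. Section 7.1.1 sends evaluation to Section 10.6, and Section 7.1.1.1 sends monitoring to Table 10-3. Section 10.6 opens by placing the discontinuation criteria in Section 7.1.1 and the investigation and monitoring in the appendix.

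This disposes of a stronger reading that a reader might infer: that the retest schedules contradict each other, so that sites cannot follow both and would run very different numbers of tests. The documents do not support it. The 2-week repeat in Section 7.1.1 is the same decision point that the table uses. A site that tests within 48 hours, twice weekly, and at 2 and 4 weeks satisfies both texts. Footnote e also leaves room to vary the schedule: "Unless an alternative monitoring schedule is agreed by the Investigator and responsible UCB Study Physician". A comparison of test counts would treat Section 7.1.1 as a stand-alone schedule, which its cross-references rule out.

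Two further replies have partial force. Section 7.1.1 only permits continuation, so an extra stopping rule in the table can be seen as an addition; but that does not settle hold versus discontinuation at week 2. The second-retest action can be read as a sequence: stop IMP, complete monitoring, then withdraw the participant. That is workable, but the reader has to construct it, and it still closes the restart route.

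The division of roles in the opening of Section 10.6 does not hold, because Table 10-3 goes on to state stopping criteria of its own and Section 10.6.2 cites both places.

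**Conclusion.** The point stands for three actions: the response to rising values in the band, the action after a failed second retest, and the 4-week stop, where the two columns of Table 10-3 differ. Nothing in the protocol ranks one text above the other for these.

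Three lesser differences should be aligned at the same time:

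- **Retest wording.** It matters mainly because both places stop IMP if the participant cannot keep to the monitoring schedule that applies. Someone able to attend at 2 weeks but not twice weekly meets one stated interval and not the other, unless an alternative is agreed.
- **Baseline condition.** It is narrow, affecting only Baseline above 2.5 × ULN, and there the table is silent rather than opposed.
- **Who is consulted.** Section 7.1.1 leaves continuation to the Investigator; the table requires discussion with the Medical Monitor.

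The documents give no rate for this finding. On an assumption of 0 to 3 of 120 participants (at most 3/120 = 2.5%), the effect on the trial's estimates is small, and the case rests on participant safety and consistent stopping. A reader might infer that the second-retest conflict alters responder status or causes a material loss of liver data. Neither is shown: IMP ends at that step under Section 7.1.1 and under the Evaluation column, Section 7.1.1.1 keeps monitoring until values settle, and all participants are to have an SFU Visit. Responder status can turn on the rising-value rule and, where a falling value counts as resolving, on the 4-week stop.

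**What to change.** Reconcile Section 7.1.1 with both columns of Table 10-3. One place should state the action when values rise within the band, the action after the second retest, and whether that action is IMP discontinuation or study withdrawal. The other place should only refer to it. The governing text should also make the table's Actions and Evaluation columns agree on the 4-week stop, say how the second-retest action fits with the rule against study withdrawal before monitoring is complete, and use one wording for the retest schedule, the entry condition and the consultation requirement.

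The sponsor's safety physician should choose the content; this review takes no view on which rule is right. The cost is protocol wording at the next amendment, or a clarification letter to sites. The schedule of visits, the sample size and the analysis methods do not change.
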